### **Exclusion**

A subject will not be eligible for this study if any one or more of the following criteria apply:

1. The subject is pregnant or breastfeeding.
2. Evidence of urethral or upper tract transitional cell carcinoma (TCC) within the past 2 years.  
Subjects with T1 disease must have no evidence of upper or lower tract disease or a more advanced stage of disease by CT urogram or MRI urogram of the abdomen and pelvis performed within 8 weeks of the first dose of study treatment. If intravenous contrast is contraindicated, retrograde ureteropyelography, or CT or MRI without intravenous contrast may be performed.
3. Subjects with hydronephrosis, except for those subjects where hydronephrosis has been longstanding (i.e., predates the diagnosis of the CIS, Ta or T1 by more than 2 years) and diagnostic evaluation at Screening shows no evidence of tumor. Subjects with hydronephrosis that is unequivocally unrelated to upper tract malignancy may be considered eligible with Sponsor approval.
4. Any intravesicular or other chemotherapy treatment within 2 weeks or any investigational agent within 4 weeks prior to the initial dose of study drug.
5. History of recurrent severe urinary tract infections (UTIs) per investigator judgment. Subjects with a current UTI requiring antibiotic treatment may defer the initiation of Vicinium treatment on Day 1 until resolution of the UTI (even if this extends the screening period requirements to start of Vicinium treatment).
6. Active, uncontrolled impairment of the urogenital, renal, hepatobiliary, cardiovascular, gastrointestinal, neurologic or hematopoietic systems which, in the opinion of the Investigator, would predispose the subject to the development of complications from the administration of intravesical therapy and/or general anesthesia.
7. The subject has a diagnosis of another malignancy within 2 years before the first dose of study treatment, except for superficial skin cancer or localized solid tumors deemed cured by surgery and not treated with systemic anticancer therapy and not expected to require anticancer therapy in the next 2 years i.e., while the subject may be taking study treatment. However, subjects with low-risk prostate cancer, e.g.:
  - Clinically localized disease ( $\leq T2a$ ) and

- Gleason score 6 (3+3) and
- Serum PSA <10 ng/mL

undergoing active surveillance may be enrolled with agreement of the sponsor.

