### **11.3 Study Withdrawal Criteria**

Subjects are free to withdraw from treatment or from any further participation in the study (i.e., withdraw consent) at any time and without prejudice to further treatment. The Investigator should discuss with the subject if they want to withdraw from further treatment only (i.e., additional data will be collected) or from all further study participation at which time no data will be collected for the subject. The investigator must withdraw a subject from all further study participation if that subject withdraws consent. No additional evaluations will be done or data collected for subjects who withdraw consent. All subjects withdrawing from further study treatment should have Post-Treatment evaluation 30 – 37 days after the last dose of study treatment and receive follow up disease evaluation (every 3 months ([Section 10.6](#)) and until a protocol-defined event as well as be contacted for data secondary endpoint (PFS, OS). The reasons and details relevant to subject withdrawal must be recorded in the case report form (CRF). The Investigator must notify the Medical Monitor if a subject is withdrawn from the study.

Subjects must be withdrawn from study drug for any of the following reasons:

- Withdrawal of informed consent
- Pregnancy ([Section 12.5](#))
- Treatment failure ([Section 14.2](#))
- Documented extravesical (i.e., upper or lower tract) urothelial carcinoma
- Development of a second malignancy that requires systemic therapy
- Cystectomy
- Unacceptable toxicity
- Persistent non-compliance with the protocol requirements
- Treating physician / study Investigator concludes that it would be in the subject's best interest
- Intercurrent illness that, in the judgment of the Investigator, may affect assessments of clinical status to a significant degree, and that requires discontinuation of study drug.
- Sponsor terminates the study.

Subjects may be considered withdrawn if they fail to return for visits, or become lost to follow-up for any other reason. Every attempt should be made to re-establish contact for subjects who are lost to follow-up (i.e., those subjects whose status is unclear because they fail to appear for study visits without stating an intention to withdraw). The Investigator should undertake appropriate due diligence and document steps taken to contact the subject (e.g., dates of telephone calls, registered letters).

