## **12.2 Concomitant Medications**

In this clinical study, Vicinium will be administered as a monotherapy. Beginning 2 weeks prior to the initial dose of study drug and throughout the time the subject is receiving Vicinium treatment, no other anti-cancer therapies that could affect the disease under study, including radiation therapy, immunotherapy, vaccine therapy, biological therapy, or gene-based therapies will be permitted with the exception that subjects who enter the study with low-risk prostate cancer undergoing active surveillance who, while on study then require androgen-deprivation therapy may be permitted to remain on Vicinium treatment with Sponsor permission. Additionally, no other investigational agent is permitted within 4 weeks before the start of study drug and throughout the time the subject is receiving Vicinium treatment.

Any other medication that is considered necessary for the well-being of the subject, and that is not expected to interfere with the evaluation of the study drug, may be given at the discretion of the Investigator.

All concomitant therapies taken from Screening until the subject has a protocol-defined event must be recorded in the subject's medical record and transcribed to the CRF.

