## 17 STATISTICS

### 17.1 General Principles of Statistical Analysis

The type I (alpha error) for all hypothesis testing will be set at 0.05, and all statistical tests will be two-sided. All confidence intervals will be two-sided 95% confidence intervals. Data will be summarized by reporting the frequency and percentage of subjects in each category for categorical and ordinal measures, and means, standard deviations (SD), medians, minimum and maximum for continuous measures.

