To evaluate biomarkers that may be associated with response or disease progression or treatment failure, which may include, for example, EpCAM status, tumor subtype morphology, furin levels in tumor cell endosomes, presence of a glycosaminoglycan coat, and presence of receptors that could impede a host anti-tumor immune response such as PD-L1.

3. **GENERAL STATISTICAL CONSIDERATIONS**

3.1. **SAMPLE SIZE AND POWER**

Assuming the true complete response rate at 12 months is 30%, sample sizes associated with various widths of a two-sided, exact (Clopper-Pearson) 95% confidence intervals are provided in the table below:

Sample Size (N)	Target Distance from P to Lower Limit	Proportion (P)	Lower Limit
121	0.080	0.300	0.220
95	0.090	0.300	0.210
76	0.100	0.300	0.200

Under the provided assumptions, a sample size of ≥ 77 evaluable subjects with early relapsed/refractory CIS with or without papillary disease is sufficient to estimate complete response rate with an exact 95% confidence interval that excludes 0.2 (PASS 2008).

The secondary endpoint of event-free survival (EFS) will be used to assess the treatment effect in all subjects, i.e., those with CIS (with or without papillary disease) and those with papillary-only disease. An estimate of EFS at the 18 month time-point will be calculated. The total sample size of 134 subjects will provide at least 80% power to test the null hypothesis that the event-free survival rate at 18 months is 20% versus the alternative hypothesis that the event-free survival rate at 18 months is $\geq 30\%$. This calculation is based on the assumptions of a nonparametric distribution for event-free survival and the length of follow-up is 24 months.

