EFS is defined as the interval from the date of first dose of study treatment to an event. Subjects who have a treatment failure or die following the post induction visit will be treated as having an event on the date of treatment failure or death. Subjects without evidence of a treatment failure who are diagnosed with upper or lower urinary tract urothelial carcinoma by histology, cytology or radiographic evidence will be censored at the date of diagnosis. Subjects without evidence of a treatment failure who undergo cystectomy will be censored at the date of cystectomy. All other subjects will be censored at the time of last assessment including long-term follow up.

Censoring rules for the analysis of EFS are presented in the table below.

Table: Censoring scheme for EFS

Situation	Date of Event or Censoring	Outcome
Treatment failure	Date of treatment failure	Event
Death without treatment failure and occurring prior to treatment discontinuation	Date of death	Event
Death without treatment failure and occurring after treatment discontinuation	Date of last evaluable disease assessment on or prior to treatment discontinuation ^a	Censored ^a
No baseline disease assessment	Date of first dose	Censored
No on-study disease assessments and no death	Date of first dose	Censored
No treatment failure and no death	Date of last evaluable disease assessment	Censored
New anti-cancer therapy received without treatment failure and reported prior to or on the same day as disease assessment	Date of last evaluable disease assessment on or prior to the date of initiation of subsequent therapy	Censored
Second non-NMIBC cancer reported prior to or on the same day as disease assessment	Date of last evaluable disease assessment on or prior to the date of diagnosis of non-NMIBC cancer	Censored
a This censoring rule acknowledges that disease assessments were not recorded after treatment discontinuation due to an AE.		

Cystectomy-Free Days

Cystectomy-free days is defined as the time from the date of first dose of study treatment to physical removal of the bladder. Subjects who are alive and do not have their bladder removed will be censored at the time of last contact.

Censoring rules for the analysis of cystectomy-free days are presented in the table below.

Table: Censoring scheme for Cystectomy

Situation	Date of Event or Censoring	Outcome
Cystectomy	Date of cystectomy	Event
Death without cystectomy	Date of death	Censored
No cystectomy	Date of last contact	Censored

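### Two undeclared SAP censoring rows can leave bladder failures out of EFS, Cohort 3 time to recurrence and PFS while the subject is still under protocol evaluation

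*SAP*

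**What the plan says.** **SAP.** Section 3.3.7 has a censoring table for EFS, one for time to disease recurrence in Cohort 3 and one for PFS. All three contain the same two rows:

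- "Second non-NMIBC cancer reported prior to or on the same day as disease assessment": censored at the last evaluable assessment on or before the date that cancer was diagnosed.
- "New anti-cancer therapy received without treatment failure and reported prior to or on the same day as disease assessment": censored at the last evaluable assessment on or before the start of that therapy.

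No type of cancer and no type of therapy is exempt.

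**Protocol.** Several such subjects may stay in the study.

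- Exclusion criterion 7 makes exceptions for superficial skin cancer and surgically cured localized tumours. Subjects with low-risk prostate cancer "undergoing active surveillance may be enrolled with agreement of the sponsor".
- Section 12.2 says that members of this last group who "while on study then require androgen-deprivation therapy may be permitted to remain on Vicinium treatment with Sponsor permission".
- Section 11.3 lists, as a reason to stop study drug, "Development of a second malignancy that requires systemic therapy". A second malignancy that needs no systemic therapy is not on that list.
- Section 14 continues the bladder evaluation every 13 weeks, also for most subjects who stop drug.

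The protocol's EFS rules (14.3 and 17.5) have two special censoring rules, upper or lower tract carcinoma and cystectomy. The SAP says in its introduction that it supersedes the protocol. SAP section 7 reports the change of primary population and states that no other changes have been described.

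**The concern.** The protocol keeps certain subjects under evaluation for the bladder endpoint, and the SAP then stops counting what the evaluation finds. Two examples show the effect on the natural reading of the tables:

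- A subject has a skin cancer excised at month 4 and CIS on biopsy at month 9. The second-cancer row censors EFS at the month 3 assessment.
- A subject under prostate surveillance starts androgen deprivation with sponsor permission, stays on Vicinium, and later fails in the bladder. The new-therapy row censors at the last assessment on or before the start of that therapy.

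The SAP's stated reason for restrictive censoring, in its event definitions and in the footnote to each table, is that assessments are not recorded after treatment discontinuation. That reason does not cover subjects who are still on drug and being assessed.

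At stake are the meaning and precision of 18-month EFS, Cohort 3 time to recurrence and PFS. A reader who relies on SAP section 7 would not learn that the SAP's EFS differs from the protocol's in this respect.

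**Working it through.** **1. The texts side by side**

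| Place | Second cancer | New anti-cancer therapy |
|---|---|---|
| Protocol 14.3 and 17.5 (EFS) | no rule | no rule |
| SAP 3.3.7, EFS text | no rule; failures after the post-induction visit are events | no rule |
| SAP 5.2.5 (EFS analysis) | no rule | no rule |
| SAP 3.3.7, tables for EFS, recurrence, PFS | censor | censor |
| SAP 3.3.7 and 5.2.2 (duration of response) | no rule | no rule |
| SAP section 7 (changes) | not listed | not listed |

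The tables thus conflict with the SAP's own EFS text, and one event is handled in two ways. If the skin-cancer subject above is a CIS responder, the month 9 CIS ends the response in the duration-of-response analysis but is not an EFS event.

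**2. Same-day findings.** The new-therapy row applies only without treatment failure, so a failure on the same day is outside it. The second-cancer row has no such qualifier. If the other cancer is diagnosed on the day of a failing assessment, both the treatment-failure row and the second-cancer row fit, and the SAP does not say which prevails.

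**3. The plan's own figure.** For EFS at month 18, SAP 3.1 sets a null value of 20% and an alternative of 30% or more. With N = 134 it claims power of 80% or higher. Protocol 17.1 sets two-sided alpha at 0.05. With a normal-approximation test of one proportion:

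- SE under the null = √(0.20 × 0.80 / 134) = 0.0346
- SE under the alternative = √(0.30 × 0.70 / 134) = 0.0396
- Power = Φ[(0.10 − 1.96 × 0.0346) / 0.0396] = Φ(0.815) = 79.3%

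This agrees with 80% to within a point. Other variants give somewhat different values, and the plan does not name its own. The censoring rows do not alter this calculation. It supplies the scale: a 10-point contrast and an SE of about 4 points.

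**4. Trigger unrelated to bladder outcome.** The documents give no trigger rate, so a range is assumed.

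*Simulation A:* N = 134, exponential EFS with 30% at 18 months, 3-monthly evaluations, triggers uniform over 24 months.

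| Affected (assumed) | SE of 18-month EFS (points) | Failures not counted by month 18 |
|---|---|---|
| 0% | 3.94 | 0 |
| 5% | 3.99 | 1.7 |
| 10% | 4.04 | 3.4 |
| 15% | 4.10 | 5.1 |

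*Simulation B:* half of the failures at the first evaluation, triggers uniform over 18 months, 2%, 5% and 10% affected. The mean estimate stays at about 30% (or about 20% when that is the true value), the SE at a true 30% is 3.9 to 4.1 points, and about 0.7 to 4 failures go uncounted.

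Both simulations carry Monte Carlo error of a few hundredths of a point in the SE. Failures are dropped, but Kaplan-Meier allows for that when censoring is independent.

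**5. Trigger related to bladder outcome: the extreme case.** Suppose every triggered subject is one who would have failed, so that k true failures are hidden, spread evenly over evaluations 2 to 6, with half of all failures at evaluation 1.

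For a true 30%, there are 134 × 0.70 = 93.8 failures: 46.9 at evaluation 1 and 9.38 at each of the next five. With k = 5, one failure is hidden at each of those five, leaving 8.38 counted. The risk sets are 86.10, 76.72, 67.34, 57.96 and 48.58, so

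S(18) = 0.65 × (1 − 8.38/86.10) × (1 − 8.38/76.72) × (1 − 8.38/67.34) × (1 − 8.38/57.96) × (1 − 8.38/48.58) = 0.324.

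| Hidden failures k | Estimate if true EFS is 20% | Estimate if true EFS is 30% |
|---|---|---|
| 1 | 20.4% | 30.5% |
| 3 | 21.1% | 31.4% |
| 5 | 21.9% | 32.4% |
| 10 | 24.1% | 35.0% |

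These values are an upper illustration. Nothing in the documents shows that triggers select future failures in this way.

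**The case against.** The strongest reply is that the SAP does not clearly discard anything. Its EFS text counts failures after the post-induction visit as events, the first row of the EFS table does the same without qualification, and SAP 5.2.5 repeats only the tract-carcinoma and cystectomy rules. With no order of precedence stated, censoring ahead of a later failure is the natural reading of the two rows but not an explicit instruction. This stands, and it makes a statement of precedence part of the fix.

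The number affected is unknown and the loss of precision is slight. Only secondary endpoints are touched. Whether to censor at other cancers or treatments is partly a choice of estimand. All of this stands too. Such a choice should still be declared, and it should fit a protocol that keeps the subjects under evaluation.

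A reader might infer three stronger things that the documents do not support:

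- **That everyone who enters with prostate cancer is censored from the start.** The word second points to a cancer arising on study. For a cancer known at entry the censoring date would fall before the first dose, and the rows that use the first-dose date cover only missing assessments and so do not settle it. The rule is undefined there. For prostate cancer the clear route is the new-therapy row.
- **That EFS is biased upward.** No passage links these triggers to bladder outcome.
- **That the protocol regards these treatments as irrelevant to the bladder.** Section 12.2 permits androgen deprivation as an exception within a ban on anti-cancer therapies that could affect the disease, and only with sponsor permission. Enrolment of these subjects also needs sponsor agreement.

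Finally, for subjects taken off drug, the SAP says assessments are not recorded, so there may be no later failure to lose. The point therefore rests on subjects who remain on drug and assessed.

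**Conclusion.** The concern holds as an inconsistency between the SAP tables and three other texts: the protocol's EFS rules, the SAP's own EFS text, and its duration-of-response rule. The change is not declared in SAP section 7.

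The size cannot be fixed from the documents and may be nil. With an assumed 5–15% of subjects triggering independently of bladder outcome, the SE of 18-month EFS goes from about 3.9 to 4.0–4.1 points and the estimate is unbiased. Upward bias arises in two situations only: the trigger is related to bladder outcome, or the second-cancer row overrides a failure found the same day. Ten hidden failures would be needed to move a true 30% to 35%, under the extreme assumption in step 5.

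The primary analyses, complete response and duration of response, use neither row and are unaffected. The change is worth making because the rows as written allow observed bladder failures to be left out, and the correction is cheap. It should not be reported as a demonstrated bias.

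**What to change.** In all three SAP 3.3.7 tables:

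1. Delete the second-cancer row, or limit it to a malignancy first diagnosed after Day 1 that requires systemic therapy, which matches protocol 11.3. This also settles cancers known at entry.
2. Limit the new-therapy row to therapy directed at urothelial carcinoma. State that androgen deprivation permitted under protocol 12.2 and local removal of a skin cancer do not censor.
3. State that a treatment failure (for PFS, a progression) on the same date takes precedence over censoring.
4. List any rule that remains in SAP section 7 as a change from the protocol.

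The cost is SAP wording and programming, with no new data collection. The EFS figure may become slightly less favourable.

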### **17.5 Analysis of Efficacy**

The primary efficacy analysis will be based on the complete response (CR) rate and duration of response in subjects in Cohort 1 (see [Section 10](#)). The number and percentage of subjects with CIS with or without papillary disease with a complete response will be summarized separately at each response assessment. Ninety-five percent (95%) confidence intervals around the complete response rate will be calculated using the Clopper-Pearson method. For subjects with CIS with or without papillary disease who achieve complete response, the duration of response, defined as the start of the complete response to the first documented case of treatment failure (see [Section 14.2](#)) or death, will be estimated using the method of Kaplan-Meier. Any subject who does not experience treatment failure or death will be censored at the last non-missing assessment.

All subjects will be included in the analysis of event-free survival (EFS). EFS will be estimated using the method of Kaplan-Meier. Protocol-defined events in the analysis of event-free survival are:

- Treatment failure (see [Section 14.2](#)). Subjects with a treatment failure that their post-Induction Phase assessment will be considered to have a treatment failure on study Day 1.
- Death (as a first event)

Subjects without evidence of a treatment failure who are diagnosed with upper or lower urinary tract urothelial carcinoma by histology, cytology or radiographic evidence as their first event will be censored in the analysis of EFS at the date of diagnosis.

Subjects without evidence of a treatment failure who undergo cystectomy will be censored in the analysis of EFS at the date of cystectomy.

Subjects who do not experience an event will be censored at the last non-missing assessment. Subjects with persistent disease during the Induction Phase (i.e., disease at the Post-Induction Phase evaluation) will be treated as having an event at Day 1. The ninety-five percent (95%) confidence

interval around the event-free survival rate at 18 months will be presented. Analyses of other time-to-event efficacy endpoints (time to cystectomy, time to disease recurrence, time to progression, progression-free survival, and overall survival) will be analyzed in a similar manner.

- Time to cystectomy: defined as the time from the date of first dose of study treatment to surgical bladder removal

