1.4. LIST OF ABBREVIATIONS

Abbreviation	
AE	adverse event
BCG	bacillus Calmette-Guérin
BIW	twice weekly
CFU	colony forming units
CIS	carcinoma in situ
CRF	case report form
CT	computerized tomography
CTCAE	Common Terminology Criteria for Adverse Events
DSMB	data safety monitoring board
ECG	electrocardiogram
FDA	Food and Drug Administration
EFS	event-free survival
EpCAM	epithelial cell adhesion molecule
MedDRA	Medical Dictionary for Regulatory Activities
mITT	modified intent-to-treat
MRI	magnetic resonance imaging
NCI	National Cancer Institute
NMIBC	non-muscle invasive bladder cancer
OS	overall survival
PFS	progression-free survival
PK	pharmacokinetics
QTc	corrected QT interval
QTcB	corrected QT interval - Bazett's correction
QTcF	corrected QT interval - Fridericia correction
SAE	serious adverse event
SD	standard deviation
SOC	system organ class
Ta	non-invasive papillary carcinoma
T1	tumor invades lamina propria
T2	tumor invades muscularis propria
TEAE	treatment-emergent adverse event
TPP	time to progression
TURBT	transurethral resection of bladder tumor(s)

2. **OBJECTIVES**

To assess the efficacy and tolerability of Vicinium when administered as a monotherapy intravesical instillation in subjects with non-muscle invasive bladder cancer - CIS, high-grade Ta or any grade T1 papillary disease or CIS plus papillary disease who failed previous treatment (i.e., not those who are intolerant) with BCG.

Primary endpoints:

Complete response rate at 3 months in subjects with CIS (with or without papillary disease) whose disease is refractory or relapsed in 6 months or less or relapsed from 6 months to 11 months following adequate BCG treatment.

Duration of response (DoR) will be estimated (Kaplan-Meier Estimate) for those subjects with CIS (with or without papillary disease) who experience a complete response.

Secondary endpoints:

- Complete response rate in subjects at 6, 9, 12, 15, 18, 21, and 24 months in subjects with CIS
- Event free survival (EFS) in all subjects
- Cystectomy-Free Days in all subjects
- Time to disease recurrence in papillary subjects
- Progression-free survival (PFS) in all subjects
- Overall survival (OS) in all subjects
- Safety and tolerability of Vicinium therapy in all subjects

Exploratory:

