Progression-free survival (PFS) will be analyzed for subjects in Cohorts 1, 2 and 3 and is defined as the time from the date of first dose of study treatment to the date of disease progression (e.g., T2 or more advanced disease) or death on or prior to treatment discontinuation, whichever occurs first. Because disease assessments are not recorded after treatment discontinuation, a death after treatment discontinuation will not be counted as an event so as not to artificially inflate PFS. Subjects without disease progression or death will be censored at the last assessment.

Censoring rules for the analysis of PFS are presented in the table below.

Table: Censoring scheme for PFS in Cohorts 1, 2, and 3

Situation	Date of Event or Censoring	Outcome
Disease progression	Date of disease progression	Event
Death without disease progression and occurring prior to treatment discontinuation	Date of death	Event
Death without disease progression and occurring after treatment discontinuation	Date of last evaluable disease assessment on or prior to treatment discontinuation ^a	Censored ^a
No baseline disease assessment	Date of first dose	Censored
No on-study disease assessments and no death	Date of first dose	Censored
No disease progression and no death	Date of last evaluable disease assessment	Censored
New anti-cancer therapy received without treatment failure and reported prior to or on the same day as disease assessment	Date of last evaluable disease assessment on or prior to the date of initiation of subsequent therapy	Censored
Second non-NMIBC cancer reported prior to or on the same day as disease assessment	Date of last evaluable disease assessment on or prior to the date of diagnosis of non-NMIBC cancer	Censored
a This censoring rule acknowledges that disease assessments were not recorded after treatment discontinuation due to an AE.		

Overall Survival (OS)

Overall Survival (OS) is defined as the time from the date of first dose of study treatment to death due to any cause. Subjects who are alive will be censored at the date of last contact.

Fridericia Corrected QT (QTcF)

$$QTcF = \frac{QT}{\sqrt[3]{RR}}$$

Bazett Corrected QT (QTcB)

$$QTcB = \frac{QT}{\sqrt{RR}}$$

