5.2.5. Additional Efficacy Analyses

The following analyses will be conducted in the mITT population, the evaluable population, the induction phase dosing compliant population, and the study dosing compliant population.

EFS will be estimated using the method of Kaplan-Meier. Subjects without evidence of a treatment failure who are diagnosed with upper or lower urinary tract urothelial carcinoma by histology, cytology or radiographic evidence will be censored at the date of diagnosis. Subjects without evidence of a treatment failure who undergo cystectomy will be censored at the date of cystectomy. All other subjects will be censored at the time of the last assessment. The ninety-five percent (95%) confidence interval around the EFS rate at 18 months will be presented.

Time to disease recurrence will be estimated separately for each cohort using the method of Kaplan-Meier. For subjects in Cohort 3, time to disease recurrence is defined as the number of days from first dose of study treatment to the first occurrence of treatment failure. Subjects who do not experience treatment failure will be censored at the last assessment.

Cystectomy-free days, time to progression, progression-free survival, and overall survival will be estimated based on the method of Kaplan-Meier.

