- 14.2.2.4.1 Histogram of Maintaining CR for at Least 1 Year Post-Induction Phase for Subjects with CR at Months 3, 6, 9, and 12
- 14.2.2.4.2 Histogram of Maintaining CR for a Duration of at Least 1 Year for Subjects with CR at Months 3, 6, 9 and 12
- 14.2.2.5 Swim-Lane Plot: Duration of Response
- 14.2.3.2 Kaplan-Meier Plot: Event-free Survival
- 14.2.4.2.1 Kaplan-Meier Plot: Cystectomy-Free Days by Cohort
- 14.2.4.2.2 Kaplan-Meier Plot: Cystectomy-Free Days for Responders vs Non-Responders
- 14.2.5.2.1 Kaplan-Meier Plot: Time to Disease Recurrence – Cohort 3
- 14.2.5.2.2 Swim Lane Plot: Time to Disease Recurrence – Cohort 3
- 14.2.6.2 Kaplan-Meier Plot: Progression-free Survival
- 14.2.7.2 Kaplan-Meier Plot: Overall Survival
- 14.3.4.1.2 Spaghetti Plot: Clinical Laboratory Assessments by Visit – Subjects with a Treatment Emergent Grade 3 or Higher Event
- 14.3.4.1.3 Scatter Plot: Alanine Aminotransferase by Visit vs. Baseline
- 14.3.4.1.4 Scatter Plot: Alkaline Phosphatase by Visit vs. Baseline
- 14.3.4.1.5 Scatter Plot: Aspartate Aminotransferase by Visit vs. Baseline
- 14.3.4.1.6 Scatter Plot: Bilirubin by Visit vs. Baseline
- 14.3.4.1.7 Scatter Plot: Creatinine by Visit vs. Baseline
- 14.3.4.1.8 Scatter Plot: Hemoglobin by Visit vs. Baseline
- 14.3.4.1.9 Scatter Plot: Leukocytes by Visit vs. Baseline
- 14.3.4.1.10 Scatter Plot: Lymphocytes by Visit vs. Baseline
- 14.3.4.1.11 Scatter Plot: Neutrophils by Visit vs. Baseline
- 14.3.4.1.12 Scatter Plot: Platelets by Visit vs. Baseline

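### Deaths before cystectomy are censored in a Kaplan-Meier analysis of cystectomy-free days, so 1 − KM overstates the incidence of cystectomy and the curve is not the proportion alive with the bladder

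*SAP*

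**What the plan says.** SAP Section 2 lists "Cystectomy-Free Days in all subjects" as a secondary endpoint. Section 3.3.7 gives the definition: "Cystectomy-free days is defined as the time from the date of first dose of study treatment to physical removal of the bladder". The sentence that follows covers only survivors: "Subjects who are alive and do not have their bladder removed will be censored at the time of last contact". The table beneath it goes further. Cystectomy is the only event, and the row "Death without cystectomy" is censored at the date of death.

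The estimator is in Section 5.2.5: "Cystectomy-free days, time to progression, progression-free survival, and overall survival will be estimated based on the method of Kaplan-Meier". The final output list in Section 12 includes "Kaplan-Meier Plot: Cystectomy-Free Days by Cohort", a second KM plot of responders against non-responders, and Tables 14.2.4.1.1 to 14.2.4.6 by population and subgroup. The 6-month output list has a cystectomy-free days table as well.

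Protocol Section 17.5 names the endpoint differently and gives no rule for death: "Time to cystectomy: defined as the time from the date of first dose of study treatment to surgical bladder removal". Neither document plans a cumulative incidence analysis or a composite of cystectomy or death. Deaths are analysed on their own: "Overall Survival (OS) is defined as the time from the date of first dose of study treatment to death due to any cause".

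**The concern.** Censoring in a KM analysis treats a subject as someone who could still have the event later. A subject who has died cannot. Censoring deaths therefore makes KM describe the cystectomy hazard as if death did not occur, and neither KM nor 1 − KM is then the probability that a reader normally wants.

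Two readings are affected:

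- 1 − KM, read as the proportion who have had a cystectomy, is too high.
- KM, read as the proportion alive with the bladder, is too high.

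The label makes the second reading likely. The protocol's time to cystectomy became cystectomy-free days in the SAP. The SAP's event-free and progression-free endpoints count deaths up to treatment discontinuation as events, and duration of response counts every death. Among the endpoints with a -free name, this is the only one in which no death counts.

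The rule feeds every cystectomy table and figure. In the responder comparison, the overstatement would differ between the two groups if their mortality differs.

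**Working it through.** **Figures in the plan.** The documents state no cystectomy rate, death rate, threshold or power for this endpoint, so there is no figure to reproduce. All rates below are assumptions.

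**Direction.** Let Λ₁ and Λ₂ be the cumulative hazards of cystectomy and of death without cystectomy.

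- KM with deaths censored estimates exp(−Λ₁).
- The probability of being alive with the bladder is exp(−(Λ₁+Λ₂)), which is never larger.
- The probability of having had a cystectomy is ∫ exp(−(Λ₁+Λ₂)) dΛ₁, which Aalen-Johansen estimates.
- At each cystectomy time, 1 − KM rises by the cause-specific KM just before that time, multiplied by cystectomies over number at risk. Aalen-Johansen uses the all-cause KM in that product, which is never larger. Hence 1 − KM is at or above the cumulative incidence. They are equal only if no death precedes a later cystectomy.

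**Size.** Assume constant hazards, with net 24-month risks c for cystectomy (25–40%) and d for death (5–15%). Then λ₁ = −ln(1−c)/24 and λ₂ = −ln(1−d)/24 per month, and at t months:

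- KM = exp(−λ₁t)
- Alive with bladder = exp(−(λ₁+λ₂)t)
- Cumulative incidence (CIF) = λ₁/(λ₁+λ₂) × [1 − exp(−(λ₁+λ₂)t)]

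At 24 months the alive-with-bladder gap reduces to (1−c)×d.

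| c / d, 24 months | KM | Alive with bladder | Gap (points) | 1 − KM | CIF | Gap (points) |
|---|---|---|---|---|---|---|
| 25% / 5% | 75.0% | 71.25% | 3.75 | 25.0% | 24.4% | 0.6 |
| 25% / 15% | 75.0% | 63.75% | 11.25 | 25.0% | 23.2% | 1.8 |
| 30% / 10% | 70.0% | 63.0% | 7.0 | 30.0% | 28.6% | 1.4 |
| 40% / 5% | 60.0% | 57.0% | 3.0 | 40.0% | 39.1% | 0.9 |
| 40% / 15% | 60.0% | 51.0% | 9.0 | 40.0% | 37.2% | 2.8 |

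Worked CIF for 30% / 10%: 24λ₁ = 0.3567 and 24λ₂ = 0.1054, so CIF = 0.3567/0.4621 × (1 − 0.63) = 0.286.

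The smallest alive-with-bladder gap is 0.60 × 0.05 = 3.0 points. The largest is 0.75 × 0.15 = 11.25 points, quoted elsewhere as 11.2. The incidence gap runs from 0.6 to 2.8 points.

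**Extrapolation to 48 months.** With the same hazards carried forward, the incidence gap is 2.0 to 7.9 points. The alive-with-bladder gap is 3.5 points (40% / 5%: 36.0% against 32.5%) to 15.6 points (25% / 15%: 56.25% against 40.6%).

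**Estimator check.** In 2000 simulated trials of 134 subjects (30% / 10% by 24 months, censoring uniform over 12–36 months), both inequalities held in every trial. Mean 1 − KM was 29.9% against a cumulative incidence of 28.5%. Mean KM was 70.1% against 63.1% alive with the bladder.

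**The case against.** **The endpoint is time to bladder removal.** Both documents define it so, and censoring deaths is legitimate for the cause-specific hazard. This stands. The fault lies in reading KM or 1 − KM as a probability.

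**The larger gap is a different estimand.** A reader might infer that the SAP claims its curve shows the proportion alive with the bladder. It never says so. That reading comes from the label, and overall survival is tabulated and plotted separately, so deaths are not hidden. This also stands, and it makes the 3.0–11.2 points a labelling matter. It does not remove the problem, because a reader cannot combine separate KM curves for cystectomy and survival to recover either probability.

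**The remaining bias is small and runs against the drug.** At 24 months it is 0.6–2.8 points. The 95% half-width for a KM of 60–75% with 134 uncensored subjects is about 7 to 8 points (1.96 × √(0.75×0.25/134) = 7.3; with 0.6×0.4, 8.3). Overstating cystectomy does not flatter the treatment.

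**The planned outputs limit the harm.** The SAP names a landmark rate only for event-free survival at 18 months. For subgroups it asks for medians, and at the assumed rates the median time to cystectomy would be about 33 to 58 months. The 24-month gaps matter when someone reads a value off the curve.

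**Four years of deaths in an elderly population.** A reader might infer this from the analysis windows, which reach Day 1501, and the subgroup cut at age 75. The documents do not establish it. The windows are data-handling bins, eligibility starts at 18, and no age distribution or death rate is given. The 24-month follow-up is stated for the event-free survival calculation, and Protocol Section 10.6 closes the study once treatment has ended and 18-month event-free survival is determined.

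**Conclusion.** The point holds as one of estimation and labelling on a secondary endpoint. With deaths censored, 1 − KM overstates the cumulative incidence of cystectomy, and the curve must not be read as the proportion alive with the bladder. The directions follow from the stated rule and need no assumed rates.

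The sizes rest wholly on the assumed constant hazards and risk ranges. At 24 months the effect on cystectomy incidence is modest, and the larger gap concerns only the reading that the label invites. The 48-month figures are pure extrapolation.

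A reader might go further and conclude that death must become an event in this endpoint. The documents do not support that: they define time to bladder removal, and adding death would redefine the endpoint. It is optional. Sample size, power, alpha and hypothesis tests are untouched. The change is still worth making because it is standard and cheap.

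**What to change.** 1. In SAP 5.2.5, and in the 14.2.4.x tables and figures, estimate cystectomy by the Aalen-Johansen cumulative incidence function with death as a competing event. Treat the cystectomy table in the 6-month outputs the same way.
2. Keep the present KM only as a cause-specific time-to-cystectomy analysis, with a footnote that deaths are censored, and do not label it a cystectomy-free probability.
3. If a cystectomy-free curve is shown, present it as a supplementary cystectomy-free survival analysis in which cystectomy or death is the event.
4. In SAP 3.3.7, align the censoring sentence, which covers only living subjects, with the table row for deaths.

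**Cost.** One SAP paragraph and a little standard programming. Overall survival already needs the death dates. A cystectomy-free survival curve would look less favourable than the current KM, while the reported cystectomy incidence would be slightly lower than 1 − KM.
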